## Interviews

**Healthcare Worker Experience:** The study team plans to explore healthcare workers experience using barrier precautions for all patient contacts vs standard of care using qualitative methodology. Questions will address five main areas: 1) understanding of the rationale for universal gloving to reduce and prevent CDI; 2) barriers and facilitators to implementing universal gloving; 3) perceptions around how the intervention influenced healthcare workers' care of and interactions with patients and other aspects of their jobs; 4) how the healthcare workers integrated universal glove donning into their regular workflow; and 5) any other issues or areas of concern around the intervention.

Qualitative focus groups of healthcare workers (physicians, registered nurses, and health technicians who have regular and direct patient contact) will be conducted at each participating unit assigned to the intervention throughout the study period. Each focus group will include up to 12 individuals. They will last about 45 minutes with moderators following a structured interview guide, adding additional probing questions to facilitate discussion. One

moderator (either the trained LSI or local RA, or a member of the Madison-based study team) will facilitate each group discussion while another trained professional will record field notes during the group to track the flow of conversation and document nonverbal behaviors. Interviews may take place either in-person, led by trained local research staff, or virtually (telephone or webinar), led by central research staff. The central research team has previous experience with virtual focus groups. Group discussions will be audio recorded (unless participants decline to be recorded, in which case field notes will be taken instead), and tapes transcribed. Qualitative analysis will be used to identify codes, categories, and themes. Participants will be asked to complete a brief, voluntary, anonymous demographics survey that the local RA will give to the participant to complete before or after the interview (e.g., along with the interview information sheet or form 10-2303). The RA will collect the surveys from the participants once the surveys are complete. Demographic characteristics will not be linked to individual participants, and only aggregate demographic information will be obtained during analysis and shared during manuscript preparation.

**Patient Experience:** The study team plans to explore patient experience with healthcare workers use of universal gloving for all patient contacts vs standard of care using qualitative methodology. Questions will address three main areas: 1) patients' perceptions of the staff's practice of universal glove donning, including positive and negative perceptions; 2) any changes in care or interactions that patients perceive were related to universal glove donning; and 3) patients' understanding of the potential benefits of the intervention.

Individual interviews with 10 patients will be conducted at each participating unit assigned to the intervention during the intervention period. Patient interviews will be conducted either by trained Madison VA staff via Microsoft Teams and/or telephone or by the trained local RA in a private setting. For patients in private rooms, the door will be closed. For patients in semi-private rooms, they will be asked if drawing the privacy curtain is adequate to meet their privacy needs, and for those granting permission the privacy curtain will be drawn. Each session will be 15-30 minutes with moderators following an interview guide, adding additional probing questions to facilitate discussion. Interviews will be audio recorded (unless participants decline to be recorded, in which case field notes will be taken instead), and tapes transcribed. Qualitative analysis will be used to identify codes, categories, and themes. Participants will be asked to complete a brief, voluntary, anonymous demographics survey before or after the interview. The RA will collect the surveys from the participants once the surveys are complete. Demographic characteristics will not be linked to individual participants, and only aggregate demographic information will be obtained during analysis and shared during manuscript preparation.

### **Cost Analysis**

**Cost:** We will conduct a cost-identification analysis to assess cost of providing the intervention. To estimate costs of the intervention of universal gloving, we will obtain cost data direct observation, estimates and consultation with the study facility. To estimate the cost of the intervention, we will calculate the cost of implementing universal gloving and the usual care barrier approach. The cost of glove supply costs will be obtained from the research team and facility. We will also estimate the supply costs associated with the usual care gloving. We will estimate supply costs by collecting glove use data. We will obtain a monthly list of supplies (i.e., gloves) issued to each participating unit in both groups from their distribution departments. To estimate the return on investment of using universal gloving, we will also estimate the potential savings that result from a decrease in *C. difficile* infections and colonization. We will compare estimated HAI costs obtained from the literature before and after the intervention. We will estimate HAI costs based on published reports.

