## 5.6 Study Evaluations

### Patient-level data

**C. difficile Acquisition:** In both the intervention and control groups, we will obtain one swab or stool sample upon admission and one swab or stool sample upon discharge to test for the presence of *C. difficile*. This outcome data will be collected on an individual patient level, but de-identified prior to reporting. These test results will not be available to healthcare workers or patients at participating sites. Acquisition will be defined as a patient who has an initial test (via stool or perirectal swab) upon unit admission that is negative for *C. difficile* and a subsequent discharge test within the same unit that is positive for *C. difficile*.

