Middleton Memorial VA Hospital in accordance with mandated U.S. regulations governing the shipment of Diagnostic Samples, Dangerous Goods and dry ice. No patient identifiers will be received by the central laboratory. Microbiological work-up for *C. difficile* will follow Clinical and Laboratory Standards Institute procedures and the use of a central microbiological laboratory to process these specimens will assure standardized microbiological (or molecular) methods and processing of the samples. Specimens will be tested for *C. difficile*, and *C. difficile* isolates will be tested for *in vitro* cytotoxin production using previously described procedures. Shipments will be tracked using a shared database stored on the VA server.

Participants (patients and staff) will not be informed of the results of the cultures. The cultures are measuring *C. difficile* colonization, not infection. There is currently no treatment for *C. difficile* colonization, and many patients who are colonized with *C. difficile* are and remain asymptomatic. Thus, informing participants of a positive *C. difficile* culture could result in undue stress and unnecessary treatments to the patient given the possibility that the colonization will remain asymptomatic. In addition, it remains unknown whether altering behaviors of healthcare workers could impact the spread of *C. difficile* from asymptotically colonized patients and thus there is no standard for how to care for a patient that is found to be asymptotically colonized. So, it is not currently useful to inform healthcare workers simply of positive cultures. However, patients that develop symptoms of *C. difficile* infection, such as diarrhea, will be cultured and treated according to the standard of care in all intervention and control units. Specimen results will be stored on a database on the VA server, unless otherwise specified in a valid DUA.

**Demographics:** In both the intervention and control groups, for patients who consented to clinical data collection, we will obtain data on demographic characteristics (age, gender, race, weight, height) from VA administrative records (e.g., Corporate Data Warehouse [CDW] files). These data will be linked to patient specimen results (e.g., *C. difficile* colonization) and stored on a shared database on the VA server, unless otherwise specified in a valid DUA.

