*Healthcare Worker Experience:* After verification of transcription accuracy, team members will use VA-approved software to facilitate data organization, coding, and retrieval. Qualitative content analysis will inductively generate codes and categories rather than using an a priori coding scheme or researcher-generated coding scheme. Line by line coding will be conducted to identify codes or statements of meaning (level I coding). Codes that emerge will be grouped into larger categories (level II, coding for themes).

*Patient Experience:* After verification of transcription accuracy, team members will use VA-approved software to facilitate data organization, coding, and retrieval. Qualitative content analysis will inductively generate codes and categories rather than using an a priori coding scheme or researcher-generated coding scheme. Line by line coding will be conducted to identify codes or statements of meaning (level I coding). Codes that emerge will be grouped into larger categories (level II, coding for themes).

*Cost:* Descriptive statistics will be used to describe nursing time frequencies and percentages. Paired t-tests will be used to compare average provider time for donning and doffing between the intervention and control units. We will use Royston's trend test to examine the monthly costs of supplies over time.

*Provider-Patient Contact Surveys:* We will compare the differences in reported contact between the intervention and control units.

*Missing data:* We will resolve all missing data using a case-wise analysis technique or multiple imputation solution.

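### The return-on-investment plan has no rule for valuing averted colonization, compares infection costs before and after instead of between randomised arms, and states only a time-trend test for supply cost

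*Combined protocol and SAP*

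**What the plan says.** The Cost Analysis text in section 5.6 opens as a costing exercise: "We will conduct a cost-identification analysis to assess cost of providing the intervention". It then adds a return on investment based on "the potential savings that result from a decrease in *C. difficile* infections and colonization". HAI costs are to be compared before against after the intervention, and the only price source is given as "We will estimate HAI costs based on published reports". The same text says that the cost of universal gloving and of usual-care barrier practice will both be calculated, using monthly glove supply lists from units in both groups.

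The Cost paragraph of section 5.7.2 describes nursing time, compares donning and doffing time between arms with paired t-tests, and for supplies says: "We will use Royston's trend test to examine the monthly costs of supplies over time". It contains no method for the savings or for the return on investment.

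On colonization, the Patient-level data part of section 5.6 says of the study tests: "These test results will not be available to healthcare workers or patients at participating sites". The Specimen collection part repeats this ("Participants (patients and staff) will not be informed of the results of the cultures") and adds "There is currently no treatment for *C. difficile* colonization". It also says that no care standard exists for a patient found to be an asymptomatic carrier.

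Section 5.2.1 randomises one intervention and one control unit at each of five sites. It describes the pre-intervention period as preparatory work and places monthly outcome collection in the intervention period.

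**The concern.** Three features leave the economic result open to choices made after the data are seen.

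First, the plan credits two benefits that lie on one causal path. Carriers are not identified to staff and not treated, so less carriage can save money in this trial only by preventing infection. If infections averted are already credited, a second credit for colonization may price some of the same infections again.

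Second, a pre-post comparison of infection costs does not use the randomisation. Any calendar change in CDI incidence or testing would be attributed to gloving, although concurrent control units are available at every site.

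Third, the stated test for supply cost asks whether spending drifts over months. The return on investment needs a different quantity: how much more the gloving units spend than the control units.

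Cost is part of the third aim, and the abstract links a change of practice to reduced CDI and its associated costs. A reader will probably treat the return on investment as part of the case for or against gloving.

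**Working it through.** The documents state no saving, unit cost or return on investment, so there is no figure to reproduce. The check asks how large an overlap could be.

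**Inputs from section 5.7.1 (illustration only)**
- Control acquisition rate: 9.7 per 1,000 patient-days.
- Intervention rate: 6.2. The section prints this with a percent sign; I read it as per 1,000 patient-days, since 9.7 × 0.64 = 6.208.
- Required patient-days per arm: 9,879.

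**Assumptions (not in the documents)**
- C: cost of one CDI episode.
- p: probability that an acquisition leads to CDI, taken as 0.05 to 0.30.
- s: share of those CDIs that fall inside the trial's infection counts, taken as 0.25 to 1.

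**Why s can be below 1.** The Unit-level data text counts hospital-onset CDI with the hospital defined as the study unit. The Patient-level data text counts CDI during admission in consenting patients. Infections after discharge or through onward transmission fall outside both.

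**Step 1: averted acquisitions.** A = (9.7 − 6.2)/1,000 × 9,879 = 34.6.

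**Step 2: saving from all resulting infections.** A × p × C = 1.73C at p = 0.05 and 10.37C at p = 0.30.

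**Step 3: add colonization at its full expected CDI cost.** The credited total is A·p·s·C + A·p·C. Divided by A·p·C, this gives an overstatement factor of 1 + s. A, p and C cancel.

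| s | Infections only ÷ true saving | Both added ÷ true saving |
|---|---|---|
| 1.00 | 1.00 | 2.00 |
| 0.75 | 0.75 | 1.75 |
| 0.50 | 0.50 | 1.50 |
| 0.25 | 0.25 | 1.25 |

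Example at p = 0.10 and s = 0.50: infections only 1.73C, true saving 3.46C, both added 5.19C, and 5.19/3.46 = 1.50.

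**Step 4: value colonization only for uncounted infections.** A·p·s·C + A·p·(1 − s)·C = A·p·C, a factor of 1.00. If colonization is given no price, nothing is counted twice, and the saving is the infections-only column.

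**Step 5: before-after comparison.** Section 5.7.1 mentions baseline-period data for revising the power calculation, but section 5.2.1 schedules monthly outcome collection only in the intervention period. The source of the 'before' infection counts is therefore not stated. The between-arm contrast is available without them.

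**Step 6: trend test.** Suppose monthly supply cost is b in a control unit and b + d in an intervention unit from the first month. The slope over months is zero in both, whatever d is. A trend test then has nothing to detect, while the required quantity is d. The text also names no patient-day denominator, so a difference in unit volume would appear as a difference in cost.

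**The case against.** The strongest reply is that this is an incomplete method and not a demonstrated error. Much of that stands.

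- A reader might infer that the benefit is in fact counted twice. The plan gives no colonization price and does not say that two savings are summed. Only infection costs are sourced, so colonization might receive no price.
- Averted colonization can be a distinct benefit. The protocol treats carriers as a reservoir, and infections that appear later or in other patients are outside the trial's counts. An infections-only figure then understates the saving by the factor s.
- A reader might price every averted colonization as a full CDI case. At assumed progression of 5%, 10% or 30%, (1 + p)/p gives 21, 11 or 4.3 times. No text proposes that price, and it would be mispricing more than double counting.
- The HAI-cost sentences might be read as a second benefit line through which CDI enters again. They read more naturally as the price source for the saving already named.
- It would be too strong to say that the extra glove cost will go unseen. The Cost Analysis text plans a cost for each approach in both groups. What is lacking is a stated analysis of the difference.
- Nor do all these gaps necessarily favour gloving. A pre-post comparison or unscaled glove spending could err in either direction.

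The reply does not remove the missing valuation and overlap rule, the stated pre-post comparison in a trial with concurrent randomised controls, or the mismatch between a trend test and a between-arm cost difference.

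**Conclusion.** The point holds as a gap in specification with a bounded consequence. By the protocol's own account, colonization has no direct care cost in this trial, so crediting it beside infections can count the same averted infection twice. The overstatement is 1.25 to 2.00 times if colonization is valued at its full expected CDI cost and s lies between 0.25 and 1. The upper end needs every resulting infection to be inside the trial's counts. There is no overstatement if colonization is unpriced or limited to uncounted infections. The values of s and p are assumptions, but the factor does not depend on p, on the CDI price or on the number of acquisitions.

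Two further changes follow directly from the text. Savings should come from the randomised contrast, and supply cost should be analysed as a difference between arms. The primary outcome and its analysis are not affected.

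**What to change.** In Cost Analysis (section 5.6):
- Base the main savings figure on CDI episodes averted, taken as the difference between randomised arms in place of before against after.
- State that averted colonization carries no direct saving.
- Show infections not already counted (after discharge, or through onward transmission) only as a separate scenario, with a stated progression probability and a range.

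In the Cost paragraph of section 5.7.2:
- Make the supply-cost analysis the glove cost per 1,000 patient-days, intervention minus control within each site, summarised over the five site pairs.
- Keep any time trend as a supplement.

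This changes wording only. Glove lists are already planned from both groups, and infection data are already collected in both. The main return on investment may be less favourable, and later infections will appear only in the scenario, so the report should say that the main figure can understate the full saving.

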## **5.1 Study Procedures**

### **5.2 Study Design**

#### **5.2.1 Experimental Design**

We will conduct this study using a pragmatic stratified-cluster randomized trial (CRT) in ten inpatient VA hospital units (acute medical, medical/surgical, or surgical inpatient acute care units). Hospital units will be randomly assigned in a 1:1 ratio: 5 units will be randomized to enact universal gloving practices (intervention) and 5 units will continue standard of care (control).

Due to resource and personnel feasibility, randomization will be stratified by location to allow for the selection of one intervention and one control unit at each site.

A 6-12-month pre-intervention period will be used to conduct preliminary work at sites including training research assistants, identifying current practices, finalizing monitoring and observation plans. Each participating unit will collect data for up to 24 months – a 24-month intervention period. During the intervention period, we will collect data on a monthly basis, including C. difficile acquisition and infection rates, other infections (CLABSI, CAUTI, MRSA), mortality, length of stay, and intervention fidelity (hand hygiene compliance and barrier precaution compliance; glove use for all patients and glove plus gown use for patients in CP isolation). These unit-level data will be obtained from aggregate reports prepared by the infection control department at each site from data they have entered into the VA Inpatient Evaluation Center (IPEC) data management system and/or from VA administrative records. Patient-level data on relevant clinical characteristics such as comorbidities, prior treatments and healthcare usage, and outcomes such as HAIs will be obtained from VA administrative records for patients who consent to stool specimen collections. We will conduct interviews/focus groups with healthcare workers throughout the intervention period and individual interviews with patients throughout the intervention period. These interviews and focus groups will explore healthcare workers' and patients' experiences with the intervention. We will also conduct patient and healthcare worker survey on provider-patient contact using a Likert scale to assess the amount of contact patients have with their healthcare workers in both the intervention and control groups.

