#### **Unit-level data**

**C. difficile Infection:** The development of *C. difficile* infection will be determined by standard clinical care which is the presence of clinical symptoms and positive laboratory results. In both the intervention and control groups, hospital-onset (HO)-CDI will be collected monthly as a unit aggregate rate. In this case, hospital refers to the study unit. Research personnel will collect these data from site personnel (i.e., infection control) at participating sites which are collected as usual standard of care. The CDC definition of HO-CDI, used by the VA, is defined as: 1) LabID Event specimen collected >3 days after admission to the facility (i.e., on or after day 4) and 2) CDI-positive laboratory assay: A positive laboratory test result for *C. difficile* toxin A and/or B, (includes molecular assays [PCR] and/or toxin assays) tested on an unformed stool specimen (must conform to the container) OR A toxin-producing *C. difficile* organism detected by culture or other laboratory means performed on an unformed stool sample (must conform to the container). The data will be uploaded to a shared database on the VA server, unless otherwise specified in a valid DUA.

**Other Healthcare-Associated Infections:** The incidence of other HAIs including: 1) catheter-associated bloodstream infection (CLABSI), 2) catheter-associated urinary tract infection (CAUTI), and 3) MRSA HAIs will be measured. HAI data will be collected monthly for both the intervention and control groups using standard CDC/VA definitions. Research staff will collect monthly aggregate data from site personnel (i.e., infection control) at participating sites which are collected as standard of care reporting to VA IPEC (inpatient evaluation center) and/or from VA administrative records. The rate will be calculated by the number of CAUTI or CLABSI per number of device days (i.e., Foley catheters or central lines)  $\div$  1,000 and the number of MRSA infections per number of patient days  $\times$  1000. The data will be uploaded to a shared database on the VA server, unless otherwise specified in a valid DUA.

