## 5.9 Withdrawal of Subjects

Sites that are unable to meet performance measures such as a) obtaining a high rate of stool samples from admitted patients and b) collecting primary and secondary endpoint data may be withdrawn from the study at the PI's discretion.

A unit may withdraw voluntarily from the study at any point. Attempts will be made to collect all data for the duration of their participation in the intervention phase regardless if they were unit randomized to the intervention or standard care group including 30-day mortality occurring after participant withdraw or termination.

Since there is a short data collection period of only 15 months, the study team does not plan to replace any units who withdraw or terminate.

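### The infection-cost comparison behind the return-on-investment estimate is stated as before-after, with no defined baseline and no control-arm contrast, although both randomised arms already supply the rates needed

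*Combined protocol and SAP*

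**What the plan says.** The Cost Analysis part of section 5.6 introduces the savings component this way: "To estimate the return on investment of using universal gloving, we will also estimate the potential savings that result from a decrease in" *C. difficile* infection and colonization. The next sentence gives the only comparison stated for it: "We will compare estimated HAI costs obtained from the literature before and after the intervention". Unit costs are to come from published reports.

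The same paragraph treats the spending side differently. It costs both universal gloving and usual care, and obtains monthly glove supplies for the units in both arms.

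On timing, section 5.2.1 says that the 6-12-month "pre-intervention period will be used to conduct preliminary work at sites including training research assistants", along with identifying current practice and settling monitoring plans. Outcome collection is placed later: "During the intervention period, we will collect data on a monthly basis". On allocation, "randomization will be stratified by location to allow for the selection of one intervention and one control unit at each site".

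On infection outcomes, the unit-level part of section 5.6 collects hospital-onset CDI monthly in both arms. For CLABSI, CAUTI and MRSA it says "HAI data will be collected monthly for both the intervention and control groups using standard CDC/VA definitions". Section 5.7.2 compares these rates between intervention and control units.

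**The concern.** Because the unit costs are taken from the literature, a difference in HAI cost between two periods can come only from a difference in HAI counts or rates. A comparison of a later period with an earlier one therefore takes in everything else that changed between them, such as testing practice, antibiotic use and case mix. The trial has a randomised concurrent comparator that removes shared changes of this kind, but the savings sentence does not call on it.

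There is also a mismatch within the return on investment. Its cost side is measured against usual care over the same months. Its savings side, as worded, is measured against an earlier period. The two would not describe the same contrast.

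What is at stake is the savings estimate under the third objective (fidelity, cost and stakeholder experience). The primary acquisition comparison and the secondary clinical comparisons do not depend on this sentence.

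**Working it through.** The plan states no savings figure, so there is nothing to reproduce. The check is first of the text and then of the mechanism.

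**1. Is the earlier period defined anywhere?**
- Section 5.6, Cost Analysis: a before-after comparison, with no dates and no arm.
- Section 5.2.1: the pre-intervention period is for preparation; monthly outcomes belong to the intervention period.
- Section 5.7.1: data from a baseline period are mentioned, but only for revising the power calculation, and the period is not described.
- Section 5.7.2, Cost: covers nursing time, donning and doffing time, and supply costs. It gives no method for HAI savings or return on investment.
- Section 5.7.2, CDI Infection Rate: refers to comparing changes between arms, but gives no starting point for the change.

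No section supplies a window or a control-arm contrast for the savings comparison.

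**2. Are the inputs for a concurrent comparison planned?** Yes. Rates are collected monthly in both arms (section 5.6) and compared between arms (section 5.7.2).

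**3. What would an uncontrolled comparison estimate?** Let *r* be the earlier rate, *T* the background rate ratio between periods, and *RR* the glove effect. Assume equal starting rates and the same *T* in both arms.
- Before-after in intervention units: apparent reduction = 1 − *RR* × *T*.
- Concurrent: control rate *rT*, intervention rate *rT* × *RR*, so reduction = 1 − *RR*.

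*T* is not in the documents; 0.8 to 1.1 is assumed purely to show direction. The value *RR* = 0.64 borrows the 36% reduction that section 5.7.1 assumes for acquisition, which is not an HAI figure.

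| *T* (assumed) | Before-after, *RR* = 1.00 | Concurrent | Before-after, *RR* = 0.64 | Concurrent |
|---|---|---|---|---|
| 0.8 | 20% | 0% | 48.8% | 36% |
| 0.9 | 10% | 0% | 42.4% | 36% |
| 1.0 | 0% | 0% | 36.0% | 36% |
| 1.1 | −10% | 0% | 29.6% | 36% |

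For example, 1 − 0.64 × 0.9 = 0.424. With fixed unit costs, the savings estimate carries the same distortion, in either direction.

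**4. What if the arms start at different rates?** Let the starting rates be *b* (control) and *a* (intervention), with no glove effect. The concurrent difference is (*b* − *a*)*T*. The between-arm difference in change is (*bT* − *b*) − (*aT* − *a*) = (*b* − *a*)(*T* − 1), which is near zero when *T* is near 1. So a controlled baseline helps with chance differences between units; an uncontrolled one does not provide this contrast.

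**The case against.** The strongest reply is that the sentence is under-specified rather than wrong. It does not restrict the comparison to intervention units. The rest of the cost plan is between-arm: supplies are collected in both groups, and section 5.7.2 compares donning and doffing time between intervention and control units. The reference to changes in CDI rates between arms leaves room for a comparison of change. Published costs could also be applied to the two-arm rates at the analysis stage, so nothing would be lost for good.

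Much of this stands. A reader might infer that the plan commits to an uncontrolled comparison in the intervention units. The documents do not say that; the bias follows only if the sentence is carried out that way. What remains is that before-after is the one comparison stated for HAI costs, and no section adds a control arm to it.

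A reader might also infer that no baseline data will exist, including no specimens from before the intervention. That goes too far. None are described, but section 5.7.1 expects some baseline-period data, and the routine sources named in section 5.6 might supply earlier infection rates. What is missing is a window and a commitment to extract them.

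Finally, section 2.0 describes decreases in CDI after the VA's 2012 prevention bundle as small and uneven. That is a reason not to assume a flat background. It gives no trend for these units, and none for CLABSI, CAUTI or MRSA.

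**Conclusion.** The concern holds as a defect in the stated savings method: a before-after comparison with no defined earlier period and no control-arm contrast, in a trial that already plans the concurrent rates. It is worth correcting because the wording, if followed without controls, would mix background change with the glove effect and set the result beside costs measured concurrently.

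The size cannot be determined from the documents. The table shows the mechanism under assumed trends and is not an estimate for this trial. The cancellation in the concurrent contrast rests on a proportional trend shared by both arms and on equal starting rates.

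Only the cost aim is affected; a reader should not carry the point over to the clinical comparisons. The conflict between the up-to-24-month collection period in section 5.2.1 and the 15 months in section 5.9 is a separate inconsistency and adds no weight here.

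**What to change.** In the Cost Analysis part of section 5.6, with a matching line under Cost in section 5.7.2, replace the before-after comparison with a concurrent one over the intervention period:

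Savings = sum over infections *k* of (control rate − intervention rate)ₖ × intervention-arm exposureₖ × published unit costₖ

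- **Exposure.** Use patient-days for CDI and MRSA, and device-days for CLABSI and CAUTI. Section 5.6 gives denominators for CLABSI, CAUTI and MRSA but none for the CDI rate, so state it.
- **Uncertainty.** Use a method that respects the site-stratified unit randomisation. A simple form uses the five within-site differences, with 5 − 1 = 4 degrees of freedom.
- **Colonization.** Include these savings only if a published unit cost is named, and base them on the between-arm difference in acquisition. The plan at present refers only to published HAI costs.
- **Baseline, if kept.** Define its window in section 5.2.1, take it from routine records for all 10 units, and compare the change between arms.

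The main version needs a revised sentence, a matching analysis line and a small extra analysis, with no new data collection beyond having patient-day and device-day totals by arm. The optional baseline needs a further extraction of routine data and a definition of its period. The drawbacks are that the savings estimate will probably be less precise than an uncontrolled one. With one unit per arm at each site, chance differences between units also remain unless a baseline is used.
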